4.6.7.10. Major Adverse Cardiovascular Events

Major adverse cardiovascular events reported by investigators are adjudicated by an independent CEC in a blinded fashion.

The CV AEs to be adjudicated include deaths due to CV cause, myocardial infarction, hospitalization for unstable angina, hospitalization for heart failure, coronary interventions (such as coronary artery bypass graft or percutaneous coronary intervention); and cerebrovascular events, including cerebrovascular accident (stroke) and transient ischemic attack.

Only adjudicated MACE will be considered as AESI. The counts and percentages of participants with adjudicated MACE may be summarized by treatment.

In addition, MACE reported by investigator may also be summarized although a MACE reported by investigator is not considered as AESI.

A listing of participants reporting MACE events, either reported by investigator or identified by the CEC, will be provided. The listing will include treatment, participants identification including the site number, date of event, type of event as reported by the investigator, type of event as adjudicated by the CEC, time from first dose of study drug to the event, and time from last dose to the event (if participant has discontinued study drug prior to the event).

4.6.7.11. Treatment-Emergent Supraventricular Arrhythmias and Cardiac Conduction Disorders

Treatment-emergent supraventricular arrhythmias and cardiac conduction disorders will be considered as AESI. The CV events will include clinically relevant rhythm and conduction disorders.

The treatment-emergent supraventricular arrhythmias and cardiac conduction disorders events will be included using the MedDRA PTs. Detailed searching criteria can be found in Section [7.6](#) (Appendix 6).

The counts and percentages of participants with treatment emergent supraventricular arrhythmias and cardiac conduction disorders will be summarized by treatment and PT nested within SMQ. The PT will be ordered with decreasing frequency within SMQ. A listing of participants with treatment-emergent supraventricular arrhythmias and cardiac conduction disorders may be provided if deemed necessary.

4.6.7.12. Major Depressive Disorder/Suicidal Ideation

The major depressive disorder/suicidal ideation or behavior will be captured as AESI. Adverse events will be searched using MedDRA PT terms. Detailed searching criteria can be found in Section [7.6](#) (Appendix 6).

The counts and percentages of participants with TEAEs will be summarized by treatment group using MedDRA PT nested within SMQ. Events will be ordered by decreasing frequency in the total LY3437943 group nested within SMQ. A listing of participants with major depressive disorder/suicidal ideation or behavior may be provided if deemed necessary.

Additionally, suicidal ideation and behavior, and depression will be assessed by the investigator via spontaneously reported AEs and through the use of the Columbia-Suicide Severity Rating Scale (C-SSRS) and the PHQ-9.

4.6.7.12.1. Patient Health Questionnaire

Total scores for the PHQ-9 range from 0 to 27 with total scores categorized as

- none (not depressed): 0 through 4
- mild: 5 through 9
- moderate: 10 through 14
- moderately severe: 15 through 19, and
- severe: 20 through 27.

Shift tables will be provided showing the counts and percentages of participants within each baseline category (maximum value) versus each postbaseline category (maximum value) by treatment.

Additionally, the following 3 outcomes of interest will be compared between treatments (based on the maximum value during baseline and postbaseline):

- any increase in depression category (ie, worsening of depression): includes participants in the none, mild, moderate, or moderately severe category during baseline and with at least 1 postbaseline measurement
- increase from No or Mild Depression to Moderate, Moderately Severe or Severe Depression: includes participants in the none or mild depression category during baseline and with at least 1 postbaseline measurement; and
- increase from Mild or Moderate Depression to Moderately Severe or Severe Depression: includes participants in the mild or moderate depression category during baseline and with at least 1 postbaseline measurement.

4.6.7.12.2. Suicidal Ideation and Behavior Solicited Through C-SSRS

Suicide-related thoughts and behaviors occurring during the entire study period, based on the C-SSRS, will be summarized by treatment group. In particular, for each of the following suicide-related events, the counts and percentages of participants with the event will be summarized by treatment group:

- died by suicide
- nonfatal suicide attempt
- interrupted attempt
- aborted attempt
- preparatory acts or behavior
- active suicidal ideation with specific plan and intent
- active suicidal ideation with some intent to act without specific plan
- active suicidal ideation with any methods (no plan) without intent to act
- nonspecific active suicidal thoughts
- wish to be dead, and
- nonsuicidal, self-injurious behavior.

In addition, the counts and percentages of participants who experienced at least 1 of the composite measures will be presented. The participants with at least 1 postbaseline C-SSRS assessment are included. The composite measure is determined at each assessment by the “yes” or “no” responses in C-SSRS categories by the study participant:

[figure not shown]
- Category 1 – Wish to be Dead
- Category 2 – Non-specific Active Suicidal Thoughts
- Category 3 – Active Suicidal Ideation with Any Methods (Not Plan) without Intent to Act
- Category 4 – Active Suicidal Ideation with Some Intent to Act, without Specific Plan
- Category 5 – Active Suicidal Ideation with Specific Plan and Intent
- Category 6 – Preparatory Acts or Behavior
- Category 7 – Aborted Attempt
- Category 8 – Interrupted Attempt
- Category 9 – Actual Attempt (non-fatal), and
- Category 10 – Completed Suicide.

Composite endpoints of suicidal ideation and suicidal behavior based on the above categories are defined below:

- Suicidal ideation: A “yes” answer at any time during study to any 1 of the 5 suicidal ideation questions (Categories 1 through 5) on the C-SSRS.
- Suicidal behavior: A “yes” answer at any time during study to any 1 of the 5 suicidal behavior questions (Categories 6 through 10) on the C-SSRS.
- Suicidal ideation or behavior: A “yes” answer at any time during study to any 1 of the 10 suicidal ideation and behavior questions (Categories 1 through 10) on the C-SSRS.

A listing contains data for each participant with suicidal ideation, suicidal behavior, or non-suicidal self-injurious behavior during the study by treatment and visit. Data from all visits are displayed, regardless of a “yes” or “no” answer, for patients with any “yes” answer for suicidal ideation, suicidal behavior, or self-injurious behavior without suicidal intent.

4.6.7.13. **CCI**

4.6.7.14. **Drug Abuse, Dependence and Withdrawal**

Subjects with drug abuse, dependence and withdrawal will be listed. Related events can be identified by searching the MedDRA PTs contained in any of the following SMQs:

- Broad and narrow terms in drug abuse and dependence SMQ (20000101) and
- Broad and narrow terms in drug withdrawal SMQ (20000102).

4.7. Other Analyses

4.7.1. Health Outcomes

The patient-reported outcome questionnaires will be analyzed using the EAS, unless specified otherwise.

Item-level missingness is dealt with as per the instrument developers' instruction.

Additional psychometric analyses may be performed by Global Patient Outcomes Real World Evidence at Lilly and documented in a separate analysis plan.

4.7.1.1. Patient Global Impression of Status for Physical Activity

The counts and percent of participants for PGIS response categories at each time point will be summarized by nominal visit and by treatment. A shift table from baseline to postbaseline of 5 PGIS response categories will be created at each postbaseline visit.

4.7.1.2. Short-Form-36 Health Survey Version 2, Acute Form

Per copyright owner, QualityMetric Health Outcomes Scoring (PRO_CoRe V2.0) will be used to derive the following domain and component scores:

- Mental Component Summary Score (MCS)
- Physical Component Summary Score (PCS)
- Physical Functioning domain (PF)
- Role-Physical domain (RP)
- Bodily Pain domain (BP)
- General Health domain (GH)
- Vitality domain (VT)
- Social Functioning domain (SF)
- Role-Emotional domain (RE), and
- Mental Health domain (MH).

For each above parameter, the raw scores will be transformed into the domain scores (t-scores) and the following analyses for the actual value and change from baseline value will be conducted on EAS:

- Descriptive summaries by treatment group, and
- analysis from MMRM (as described in Section 4.3.2)/ANHECOVA model (as described in Section 4.3.3) depending on whether there is more than 1 postbaseline response variables. The multiple imputation will use only hypothetical strategy to deal with ICE if ANHECOVA model is used.

4.7.1.3. Eating Inventory

The following domain and component scores related to eating behavior will be derived based on the 51-item Eating Inventory questionnaire:

- dietary restraint (21 items)
- disinhibition (16 items), and
- perceived hunger (14 items).

For each above parameter, the raw scores will be transformed into the domain scores and the following analyses for the actual value and change from baseline value will be conducted:

- descriptive summaries by treatment group, and
- analysis from MMRM (as described in Section 4.3.2)/ANHECOVA model (as described in Section 4.3.3) depending on whether there is more than 1 postbaseline response variables. The multiple imputation will use only hypothetical strategy to deal with ICE if ANHECOVA model is used.

Subjects who do not speak English as their native language may have missing baseline data and will be excluded from this analysis.

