Fasting Visit	X	X		X	X	X	X	X	X	X	X			X			X	X	X		X	
Telephone Visit												X	X		X	X						
Sitting vital signs (3 measures of BP and PR)	X			X	X	X	X	X	X	X	X			X			X	X	X		X	
	Vital sign measurements should be taken before obtaining an ECG tracing and before collection of blood samples for laboratory testing, per the instruction in Section 10.8.																					
Orthostatic vital signs				X					X		X			X			X					
	1 measurement of BP and PR in supine and standing position. See Section 10.8.																					
Physical examination	X																					
12-Lead electrocardiogram				X		X	X	X	X		X			X			X		X		X	
	ECG measurements should be obtained per the instructions in Section 10.8. Electrocardiograms should be obtained prior to collection of blood samples for laboratory testing, including PK samples.																					
Participant Education and Assessment																						
Diet, physical activity counseling			X	X	X	X	X	X	X	X	X	X	X	X	X	X						
	Three-day diet and exercise diary should be reviewed as part of the counseling.																					
Patient-Reported Outcomes (PROs)																						
Patient Global Impression of Status for Physical Activity				X							X						X		X			
SF-36v2 acute form				X							X						X		X			
Eating Inventory				X							X						X		X			
	If a PRO questionnaire is not available in the native language of a participant at baseline, that questionnaire will not be administered for that participant for the duration of the trial (Appendix 10.11)																					

	Study Period I Screening			Study Period II Treatment															99	ED	Study Period III Post- Treatment Safety Follow-Up	
	1	2	3	4	5	6	7	8	9	10	11	12	13	14	15	16	17	48			801	
Visit (see Notes below)																						
Week of Treatment	-6	-3	-1	0	1	4	8	12	16	20	24	28	32	36	40	44	48	48			4 Wks post end of TXP	
				Titration period																		
Allowable Interval Tolerance (days)	±7	±7	±7	-	±2	±3	±3	±3	±7	±7	±7	±7	±7	±7	±7	±7	±7	±7			±7	
Fasting Visit	X	X		X	X	X	X	X	X	X	X			X			X	X	X		X	
Telephone Visit												X	X		X	X						
Mental Health Questionnaires																						
Patient Health Questionnaire-9 (PHQ-9)	X			X				X			X			X			X	X	X		X	
	PHQ-9 is self-administered and should be completed after assessment of adverse events.																					
Columbia-Suicide Severity Rating Scale (C-SSRS) (Baseline/Screening Version)	X																					

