10.11. Appendix 11: Patient-Reported Outcomes

When feasible, the self-administered questionnaires will be translated into the native language of participants, linguistically validated and administered according to the SoA (Section 1.3). The language of the signed ICF will be considered the participant's native language. If a translation is not available in the native language of a participant at baseline, the questionnaire(s) will not be administered for that participant for the duration of the trial. If PRO questionnaires are not collected due to a translation not being available, this will not be considered a protocol deviation.

When the PROs are collected as per the SOA, the questionnaires should be completed before the participant has discussed their medical condition or progress in the study with the investigator and/or site staff, if the participant is not adversely affected by their fasting condition.

- ***Patient Global Impression of Status for Physical Activity***

Study participants will be asked to complete a Patient Global Impression of Status (PGIs) for Physical Activity item specifically developed for this study. This is a participant-rated assessment of current limitation on physical activity due to health and is rated on a 5-point scale ranging from “1 - not at all limited” to “5 - extremely limited.”

- ***Short Form-36 version 2 Health Survey acute form, 1-week recall version***

The SF-36v2 acute form, 1-week recall version is a 36-item generic, participant-administered measure designed to assess the following 8 domains:

- Physical Functioning
- Role-Physical
- Bodily Pain
- General Health
- Vitality
- Social Functioning
- Role-Emotional, and
- Mental Health.

The Physical Functioning domain assesses limitations due to health “now” while the remaining domains assess functioning “in the past week.” Each domain is scored individually and information from these 8 domains are further aggregated into 2 health component summary scores: Physical Component Summary and Mental Component Summary. Items are answered on Likert scales of varying lengths (3-point, 5-point, or 6-point scales). Scoring of each domain and both summary scores are norm-based and presented in the form of T-scores, with a mean of 50 and SD of 10; higher scores indicate better levels of function and/or better health (Maruish 2011).

- ***Eating Inventory***

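### SAP 4.7.1.3 excludes participants from the Eating Inventory analysis by native language, while the protocol withholds the questionnaire only where no translation is available, so any translated scores collected would be dropped

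*SAP*

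**What the plan says.** **SAP.** Section 4.7.1 sets the default for patient-reported outcomes: "The patient-reported outcome questionnaires will be analyzed using the EAS, unless specified otherwise". Section 3 defines that analysis set without reference to language. Section 4.7.1.3 then plans descriptive summaries and an MMRM or ANHECOVA analysis of each Eating Inventory domain, and closes with: "Subjects who do not speak English as their native language may have missing baseline data and will be excluded from this analysis". The SF-36v2 section (4.7.1.2) has no language exclusion and states that "the following analyses for the actual value and change from baseline value will be conducted on EAS". The section on the global impression item (4.7.1.1) has none either.

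**Protocol.** Appendix 11 (section 10.11) plans for translation: "When feasible, the self-administered questionnaires will be translated into the native language of participants, linguistically validated and administered according to the SoA". It then gives the condition for withholding: "If a translation is not available in the native language of a participant at baseline, the questionnaire(s) will not be administered for that participant". The note in the Schedule of Activities (section 1.3) repeats this one questionnaire at a time: "If a PRO questionnaire is not available in the native language of a participant at baseline, that questionnaire will not be administered for that participant". Appendix 11 also fixes what native language means: "The language of the signed ICF will be considered" the participant's native language.

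**The concern.** The protocol asks whether a translation is available. The SAP asks whether the participant's native language is English. The two questions give the same answer only if no translated Eating Inventory was ever used.

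The protocol intends translated, linguistically validated forms to be given where feasible. A participant with such a form would complete the Eating Inventory at Weeks 0, 24 and 48. The SAP sentence would then remove that participant, although baseline and follow-up scores exist. The only reason it offers is possible missing baseline data, and that reason does not apply to someone who has a baseline score.

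At stake are the precision of an exploratory comparison, the population to which it applies, and its comparability with the SF-36v2 results reported beside it.

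**Working it through.** **1. Is this superseded text?** No. The SAP says it is based on the protocol dated 21 May 2021. The protocol's amendment history shows that this amendment added the translation rule to the Schedule of Activities and Appendix 11. The SAP sentence was therefore written against a protocol that already held the rule.

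**2. The two criteria side by side.** Native language is read here as the language of the signed consent form, as the protocol defines it.

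| Participant | Protocol: form given? | SAP as written: analysed? |
|---|---|---|
| Native language English | Yes | Yes |
| Other language, translation available at baseline | Yes | **No** |
| Other language, no translation at baseline | No | No |

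The documents conflict only in the middle row. In the last row the language exclusion adds nothing: the planned models take the baseline value as a covariate, and no change from baseline can be formed without it.

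The SAP section does not itself cite the consent-form definition. Read by mother tongue instead, it could also drop a participant who signed an English consent form and completed the English questionnaire.

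**3. Size.** The plan states no figure for this point, so there is none to reproduce. The inputs are:
- Total randomised: about 300 (protocol section 9.2). The 2:1:1:1:1:2:2 ratio sums to 10, so each pooled dose and placebo has 300 × 2/10 = 60.
- f, the share of otherwise analysable participants who have usable scores but are excluded by language: not given in either document. The values below are assumptions.

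If f is the same in every arm and the residual variance does not change, each arm shrinks from n to n(1−f). The standard error of a dose-placebo difference is then multiplied by 1/√(1−f).

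| Assumed f | Participants dropped (300 × f) | Factor 1/√(1−f) | Increase in standard error |
|---|---|---|---|
| 0 | 0 | 1/√1.00 = 1.000 | 0% |
| 5% | 15 | 1/√0.95 = 1.026 | 2.6% |
| 10% | 30 | 1/√0.90 = 1.054 | 5.4% |
| 20% | 60 | 1/√0.80 = 1.118 | 11.8% |
| 30% | 90 | 1/√0.70 = 1.195 | 19.5% |

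The counts use all randomised participants, so they are upper figures once dropout is allowed for. The zero row is a real possibility, because the protocol promises translation only where feasible and foresees forms not being collected.

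**4. Direction of any bias.** Consent-form language and the availability of a translation at baseline are both settled before randomisation. Excluding on either does not in itself unbalance the arms.

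**The case against.** The strongest reply is that the sentence only explains why some participants drop out. On that reading, people without an English form lack a baseline score and so cannot enter a change-from-baseline analysis, and the SAP already does what is wanted. This may well be the intent. It is not what the sentence says: it makes missing baseline data a possibility for the group and exclusion a certainty for the whole group.

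A second reply is that perhaps only the English Eating Inventory was used, in which case nobody with data is lost. That stands, and it is why the loss has to be stated from zero upward. A reader might infer that completed translated questionnaires are actually being thrown away. The documents do not support that, because neither says that a translated Eating Inventory existed or was given to anyone.

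A third reply concerns the SF-36v2. The protocol rule works questionnaire by questionnaire, so a translation gap for the Eating Inventory alone would explain why only that section has a language caveat. That also stands. The contrast shows that the two analyses may cover different participants; it does not by itself prove an error.

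Finally, if the protocol's definition of native language carries over to the SAP, only participants who signed a consent form in another language are affected. That limits the group but leaves the mismatch in place.

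**Conclusion.** The mismatch is real and can be seen from the text alone. As written, the SAP would discard collected Eating Inventory scores from any participant who completed a translated version. Whether any did is not stated. The increase in standard error is 0% if none did, about 5% if 10% of analysable participants did, and about 12% if 20% did. The shares are assumed, and the figures rest on equal shares across arms and unchanged variance.

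The point is minor. Eating Inventory domain scores are exploratory, and no primary, secondary or safety result depends on them. A reader might go further and infer that the exclusion biases the comparison with placebo. The documents do not support this, since the excluding trait is fixed before randomisation. The cost is precision, and a result that covers fewer participants than the default analysis set for patient-reported outcomes.

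**What to change.** Replace the last sentence of SAP section 4.7.1.3 with:

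> Participants without a baseline Eating Inventory score (for example, because no translation was available) are excluded from the change-from-baseline analysis; all participants with a baseline score are included, whatever their language.

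If no translation was used, and native language means consent-form language, this gives the same participants as the present wording. If a translation was used, it keeps randomised data that were collected. It would also help to report, by arm and language, how many participants were not given the questionnaire. If an English-only analysis is deliberate, for instance because of doubts about the comparability of translations, the SAP should say so and give that reason.

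The cost is one sentence in the SAP. The protocol rule needs no change, and protocol section 9.4.5 leaves the details of exploratory analyses to the SAP.

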4.7.2. Subgroup analyses

Subgroup analyses of the primary endpoint will be made to assess consistency of the intervention effect across the following subgroups:

- age group: younger than 65 versus 65 years or older
- race
- sex: female versus male
- ethnicity
- BMI (kg/m^2) group: less than 30 versus greater than or equal to 30 and less than 35 versus greater than or equal to 35 and less than 40 versus greater than or equal to 40, and
- baseline BMI (the minimum or greater to less than the first quartile, the first quartile or greater to less than the median, the median or greater to less than the third quartile, the third quartile or greater to the maximum).

For each subgroup analysis, MMRM model as described in Section 4.3.2 will be used.

If the number of participants is too small (less than 10%) within a subgroup, then the subgroup categories may be redefined prior to unblinding the study. Additional subgroup analyses may also be performed.

